#### Risk of Generation of an Immune Response to Normal Cells

It is unknown whether generating an immune response to specific proteins will have any effect on normal cells.

- We will be monitoring closely for signs of immune damage to normal cells. We will be looking for diarrhea, development of any unusual rashes and changes in liver, kidney, and blood function through blood tests.
- Medicine may be administered if patients develop any autoimmune symptoms.

Likely	Less likely	Rare, some may be serious
None	
Skin rashes
 
Diarrhea
	A severe autoimmune reaction which could cause death

#### Allergic Reaction Monitoring

Severe allergic reactions are not common, but they do occur. If they occur, they tend to happen within an hour of exposure to the substance causing the allergy. Because of this rare risk, patients will be observed in the clinic for a minimum of one hour after each vaccine to make sure there are no immediate side effects or allergic reactions. While other rare systemic allergic reactions (i.e., generalized skin rash) may occur

within 24 hours they are rarely associated with life-threatening adverse events that would require emergency treatment. To date, aside from the expected and transient vaccine-related side effects of injection site redness, warmth, edema, induration with or without tenderness and occasionally malaise, low-grade fever, and arthralgia we have not observed any allergic-type or anaphylactic reactions. Furthermore, in our recently completed phase I DNA vaccine study of 66 patients, who were immunized with the same plasmid construct, proposed in this study, there were no related grade 3 or 4 AEs observed within the first 24 hours.

Should an allergic reaction occur, treatment per standard of care will be implemented. If symptoms of a mild vaccine-related reaction occur, such as a skin rash or itching, the study doctor may treat the patient with acetaminophen or diphenhydramine if clinically indicated. Vital signs will be taken at 60 minutes, with a window of between 55 and 75 minutes, post immunization and as indicated.

### **6.3 Availability**

WOKVAC for clinical use will be amplified, quantified and vailed by the Biologics Production Facility at the Fred Hutchinson Cancer Research Center under good manufacturing practice (GMP) laboratory conditions.

RhuGM-CSF is a sterile, white, preservative-free lyophilized powder in 250 mcg vials and is obtained by commercial suppliers and stored at their specifications.

The vaccine will be supplied as frozen vials and each vial will carry a label bearing the drug identification and conditions for storage. The site pharmacy will prepare and dispense the drug for administration per a standard operating procedure established by the UW Investigational Drug Services (IDS).

The site pharmacy will prepare and dispense the drug for administration per a standard operating procedure established by the UW IDS by pulling a single vial vaccine from the freezer and thawing it slowly at room temperature. The GM-CSF (rhuGMCSF, Sargramostim) will be reconstituted in sterile preservative free water. The GM-CSF (rhuGMCSF, Sargramostim) will be added to an empty vial and then the vaccine is added to that. The vial is rotated gently to mix. The dose will be divided into Tuberculin Safety Syringes with a 27 gauge,  $\frac{1}{2}$  inch needle with no more than 0.33ml each for intradermal injection.

### **6.4 Agent Distribution**

WOKVAC will be managed by the University of Washington Investigational Drug Service (UW IDS). UW IDS will be responsible for the study drug disposition (drug receipt, transfer or return) and shall be documented on the Investigational Drug Accountability Record. UW and UWI will each obtain the adjuvant, GM-CSF (rhuGM-CSF; Sargramostim;) directly.

The prepared vaccine will be stored at the FHCRC Biologics Facility until it is transported to the University of Washington Investigational Drugs Services (IDS) where it will either be dispensed to UW patients or shipped to UWI.

Vaccine shipped to UWI will be sent overnight on dry ice. Once received at UWI the chain of custody documentation should be completed and the vaccine stored in the freezer per label specifications. We are planning 2 shipments over the study, but if an additional request needs to be made UWI should contact UW IDS using the contact information below:

Investigational Drug Services  
Reference Study Number: CRC# 9983  
[contact]  
[contact]

## **6.5 Agent Accountability**

The Investigator, or a responsible party designated by the Investigator, must maintain a record of the inventory and disposition of all agents received. The Investigator is required to maintain adequate records of receipt, dispensing and final disposition of study agent. This responsibility has been delegated to UW IDS as well as dispensing records by the site pharmacy. Include on receipt record from whom the agent was received and to whom study agent was shipped, date, quantity and batch or lot number. On dispensing record, note quantities and dates study agent was dispensed.

## **6.6 Packaging and Labeling**

WOKVAC will be packaged by the Biologics Production Facility at the Fred Hutchinson Cancer Research Center under GMP laboratory conditions. The vaccine will be vialed as single doses containing DNA suspended in tromethamine/EDTA (TE) as a stabilizing buffer of each of the three study doses. The vaccine formulation is labeled to accurately reflect the product identity, concentration, lot number and fill date. These labels are attached to vials immediately post-fill.

## **6.7 Storage**

Vials of the vaccine will be subjected to microbial, sterility and stability testing to ensure safety and stored at -20°C +/- 5°C until use. The product will be stored in freezers with alarmed temperature controls at both the FHCRC Biologics Facility and site pharmacies at temperature -20°C ± 5°C.

The GM-CSF (rhuGMCSF, Sargramostim) will be stored per package insert. It should be stored at 2-8°C (36-46°F). It should not be frozen or shaken.

## **6.8 Registration**

All patients who sign an informed consent form are assigned a patient identification number (PID). These numbers are assigned sequentially and designate the recruitment site, the study and the patient. These numbers will be provided to the site in a Registration Log provided by the Consortium Lead Organization (CLO-UWI) at the time of study initiation.

University of Washington: Once screening is complete, and the patient is determined to be eligible, UW will [contact]) or email ([contact]) to the UWI during normal business hours (M-F 8:00 am - 4:15 pm Central Time), the following information:

Signed Informed Consent Form	Eligibility Questionnaire
Baseline Visit Guide	Physical Exam and Vital Sign Form
Med/Surg History Assessment	Baseline Symptom Assessment
Concomitant Medication Worksheet	Hematology and Chemistry Lab Results
Prior Breast Cancer History	

The CLO-University of Wisconsin will confirm eligibility, the registration number and the dose level. UWI will email a confirmation of the registration to the Consortium PI, Study PI's, Co-Investigators and Study Coordinators.

University of Wisconsin: Once screening is complete, and the patient is determined to be eligible, the University of Wisconsin will email a confirmation of the registration to the Consortium PI, Study PI's, Co-Investigators and Study Coordinators.

The Study Coordinator at the CLO-UWI will email the study coordinator at UW once/week for an update on screening efforts for UW and to provide information about screening efforts at UWI.

#### **6.9 Blinding and Un-blinding Methods**

This is not a blinded study.

#### **6.10 Agent Destruction/Disposal**

UW IDS will be responsible for the study drug disposition and shall be documented on the Investigational Drug Accountability Record. The disposal of research trial materials that are in UW IDS pharmacy will be incinerated under a state contract through an Environmental Protection Agency (EPA) licensed facility.

UWI should return empty and unused vaccine to the UW IDS for destruction and disposal. This will also serve as a double check of the product inventory.

## 7. CLINICAL EVALUATIONS AND PROCEDURES

### 7.1 Schedule of Events

Evaluation/ Procedure	Baseline 	1 st vaccination	2 nd , 3 rd vaccination 	Post-vaccination Follow-up Visits 	Long-term Follow-up 
Informed Consent	X				
Assess Eligibility	X				
Medical History	X				
Baseline Symptom Assessment	X				
Physical Exam 	X		X	X	
Vital Signs/ and Weight	X	X	X	X	
Concomitant Medications	X	X	X	X	
Assign dose arm	X				
Urine Pregnancy Test 	X	X	X		
CBC 	X	X 	X	X	
CMP 	X	X	X	X	
HbA1c	X			X	
GAD65		X		X	
ANA, anti-dsDNA, C3 and TSH		X	X	X	
Research Blood 		X		X	
Tetanus- diphtheria Immunization 		X			
MUGA/ECHO 	X		X	X	
Symptom Assessment/ Adverse Events		X	X	X	
Dispense Study Vaccine		X	X		
60 minutes post vaccine vitals 		X	X		
Medical Record Chart review					X 

Must occur within 3 weeks (21 days) of 1st vaccination with the exception of CMP, CBC, HbA1c and ECHO/MUGA which must be in acceptable range within 90 days of enrollment

Physical Exam includes: Weight, vital signs, symptom/toxicity assessment, and ECOG scoring

Performed on females who are having sex that could lead to pregnancy.

Complete blood count (CBC) includes differential and platelets.

Complete blood count (CBC) with differential and platelets does not need to be drawn if completed within 90 days of enrollment.

Comprehensive Metabolic Panel (CMP) includes serum electrolytes, creatinine, BUN, AST, ALT, alkaline phosphatase, and total bilirubin. For vaccine visits follow glucose monitoring per section 8.5.1.1.

During the consent process, and at subsequent visits, patients will be instructed to hydrate sufficiently prior to visits requiring large volume blood draws.

Tetanus-diphtheria immunization only given if patient has not received one within 6 months.

MUGA or ECHO to determine LVEF will be performed at baseline (if not completed within 90 days of prior to enrollment), prior to 2nd vaccination and 1 month post study treatment. Once a patient has had the baseline LVEF results, the same monitoring modality should be used for all subsequent LVEF evaluations. The MUGA/ECHO prior to 2nd vaccination and at 1 month post can be performed within 1 week of their scheduled visit.

Vaccines are scheduled 28 (+7) days from the previous vaccine.

The 1-month post vaccine visit should occur 28 (+7) days following the last vaccine. The 6-month post vaccine visit should occur 168 ( $\pm$  14) days following the last vaccine.

Follow-up includes requesting MD notes, clinical labs and imaging reports.

 60 minutes Post vaccine vitals may be collected 55-75 minutes after vaccination.

 Long-term follow up data, beyond the 6 month follow-up visit, will be kept and managed by the IND Sponsor (University of Washington).

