A Phase I study of pUMVC3-IGFBP-2 is currently underway in 25 patients with ovarian cancer. 208 AEs have been collected to date (representative of 86 vaccine administrations in 25 patients) and 96% of the AEs were grade 1 or grade 2. Similar to the HER2 ICD vaccine, injection site reaction and fatigue, each comprising 12% of all AEs, were the most common complaints. All injection site reactions and 79% of reports of fatigue were considered related to vaccination. Mild changes in immune serologies, including one patient with a transient decreased complement C3 and one patient with a positive ANA defined by titers of  $\geq 1:160$  by IF, have occurred with no associated symptoms. There was no significant vaccine induced cardiac toxicity in this study. One patient reported Grade 1 palpitations that lasted for 2 days and was recorded as possibly related.

Studies performed to date evaluating immunization to IGF-1R in a genetically engineered model of human breast cancer in mice (TgMMTV-neu) show no evidence of histologic immunity or changes in blood chemistries or blood counts. These data are similar to what we have generated previously in the preclinical development of HER2 and IGFBP-2 as vaccine candidates.

Our pre-clinical studies of WOKVAC in mice have not demonstrated clinical signs of toxicity. Specifically, complete blood counts, electrolytes, glucose and liver function test remained within normal range and there was no evidence of autoimmunity by pathologic survey of organs. Regardless, all patients on study will be evaluated for acute autoimmune toxicity prior to each vaccination and at 1 and 6 months after the last

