Clinical and autoimmune labs will be drawn prior to each vaccine and 1 month and 6 months following the last vaccine to evaluate for safety. Patients are monitored for the development of toxicities by assessing adverse events (AE's) with serum chemistries, liver function studies, and complete blood counts. Adverse events for all systems are graded on a scale of 1-5 using the Common Terminology Criteria for Adverse Events Version 4.0 (CTCAE v4.0). We will be using the Cancer Therapy Evaluation Program (CTEP), National Cancer Institute (NCI) Guidelines for reporting adverse events assigning attribution (unrelated, unlikely, possible, probable, definite) Blood samples to test the effect on the immune system will be drawn at baseline, and 1 month (28±7 days) and 6 months (168±14 days) following the last vaccine. The specific measurements being done to evaluate immune response are memory T cell response, modulation of Treg, and MDSC.

The duration of the study will be 5 years, which includes annual follow-up from enrollment, with the subject's primary oncologist or primary care physician. Long-term follow up data, beyond the 6 month follow-up visit, will be kept and managed by the IND Sponsor at the University of Washington.

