## 4. PATIENT SELECTION

### 4.1 Inclusion Criteria

- 4.1.1. Patients with non-metastatic, node positive, HER2 negative breast cancer, confirmed by pathology report, who are in remission and defined as having no evidence of disease (NED). HER2 negative is defined as
  - a. 0-1+ HER2 expression by immunohistochemistry (IHC) OR
  - b. Fluorescence in situ hybridization (FISH) negative OR
  - c. HER2 2+ and FISH negative
- 4.1.2. Patients must be at least 28 days post cytotoxic chemotherapy, radiotherapy, monoclonal antibody and/or other biologic therapy, prior to enrollment. Patients on bisphosphonates, denosumab, and/or

endocrine therapy administered during the study are eligible and may continue throughout duration of study.

- 4.1.3. Patients must be at least 28 days post systemic steroids prior to enrollment.
- 4.1.4. Patients must be at least 18 years of age.
- 4.1.5. Patients must have Eastern Cooperative Oncology Group (ECOG) Performance Status Score of  $\leq 2$ .
- 4.1.6. Adequate laboratory values within 90 days of enrollment defined as follows:
  - a. White blood cell (WBC)  $\geq 3000/\text{mm}^3$
  - b. Hemoglobin (Hgb)  $\geq 10 \text{ g/dL}$
  - c. Lymphocyte count  $\geq 800/\text{mm}^3$
  - d. Platelet count  $\geq 75,000/\text{mm}^3$
  - e. Serum creatinine  $\leq 2.0 \text{ mg/dL}$  or creatinine clearance  $> 60 \text{ ml/min}$
  - f. Total bilirubin  $\leq 1.5 \text{ mg/dL}$
  - g. Aspartate aminotransferase (AST)/Serum glutamic oxaloacetic transaminase (SGOT)  $\leq 2$  times upper limit of normal (ULN)
  - h. HbA1c  $< 5.7\%$
- 4.1.7. Patients must have recovered from major infections and/or surgical procedures, and in the opinion of the investigator, not have any significant active concurrent medical illnesses precluding protocol treatment.
- 4.1.8. The effects of WOKVAC on the developing human fetus are unknown. For this reason, patients who are having sex that can lead to pregnancy must agree to use adequate contraception (hormonal, barrier method of birth control, or abstinence) for the duration of study participation. Should a woman become pregnant while participating in the study, she should inform her study doctor immediately and will not receive any more study treatment.
- 4.1.9. LVEF results must be  $\geq$  lower limit of normal (LLN) for institution performing based on results from the MUGA or ECHO done at baseline.

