## **7.2 Baseline Visit (may be performed up to 3 weeks prior to 1st vaccination)**

Baseline evaluations determine if the patient is an eligible candidate for study participation and establish the patient's health status at the time of study entry. Standard-of-care laboratory evaluations done prior to signing consent will qualify for baseline evaluations if they have been conducted within 90 days prior to enrollment. Standard-of-care MUGA or ECHO done prior to signing consent will qualify for baseline evaluations if conducted within 90 days prior to enrollment. All baseline evaluations must be completed before study agent is dispensed. If a study patient is found to be ineligible any blood collected for research purposes will be destroyed. The destruction of the blood will be clearly documented in the documented study records.

- 7.2.1. Sign informed consent prior to any study-specific baseline testing
- 7.2.2. Medical history and complete physical examination which includes weight, vital signs, baseline symptom assessment, review of concomitant medications, and ECOG scoring (Appendix A)
- 7.2.3. MUGA or ECHO
  - a. LVEF must be  $\geq$ LLN per institution performing the test, to allow the patient to continue with vaccination
- 7.2.4. Patients will have the following tests and procedures completed prior to the first vaccine.
  - a. Clinical labs
    - i. Complete blood count (CBC) with WBC differential, hemoglobin and platelet count
    - ii. Comprehensive metabolic panel (CMP) which includes electrolytes, glucose, creatinine, blood urea nitrogen (BUN), AST (SGOT), ALT, alkaline phosphatase, and total bilirubin
    - iii. HbA1c
- 7.2.5. Urine pregnancy testing will be performed on female patients who are having sex that could lead to pregnancy. If a patient is found to be pregnant, she will not be able to participate in the study.

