## **7.3 First Vaccination**

- 7.3.1. Patients will have the following tests and procedures completed prior to the first vaccine:
  - a. Vital signs
  - b. Complete blood count (CBC) with WBC differential, hemoglobin and platelet count if not completed within 90 days of enrollment

- c. Comprehensive metabolic panel (CMP) which includes electrolytes, glucose, creatinine, blood urea nitrogen (BUN), AST (SGOT), ALT, alkaline phosphatase, and total bilirubin (within 2 days of visit is allowable)
  - i. Review non-fasting glucose value prior to vaccine administration then follow Section 8.5.1.1 to determine whether vaccine can be administered
- d. ANA, anti-ds DNA, C3, TSH
- e. GAD65
- f. Urine pregnancy testing if applicable

7.3.2. Approximately 200 ml of blood (about 1 cup) will be collected for immunologic monitoring, prior to the first vaccine. It is possible that this volume of blood loss could cause the patient to feel lightheaded or dizzy. If clinically indicated, IV fluids will be administered

7.3.3. Tetanus diphtheria (Td) immunization if one has not been administered within six months and used as a positive control for immune responses. If patient has a history of an allergic reaction to the Td immunization, one will not be given and patient can still continue to be in the study as there are other positive controls used for immune assays.

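### The blood count at the first vaccination can be waived for one taken up to 90 days before enrollment, against Sections 2.2 and 3, so the pre-vaccine reference count may be stale

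*Combined protocol and SAP*

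**What the plan says.** The waiver stands in two places. Footnote 5 of Section 7.1 says that the CBC at the first vaccination "does not need to be drawn if completed within 90 days of enrollment", and Section 7.3.1.b asks for it only "if not completed within 90 days of enrollment".

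Three other provisions decide how old that CBC may be.

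- Footnote 1 of Section 7.1 sets a 21-day limit for baseline procedures, but "with the exception of CMP, CBC, HbA1c and ECHO/MUGA which must be in acceptable range within 90 days of enrollment".
- Section 7.2 accepts standard-of-care labs done before consent: they "will qualify for baseline evaluations if they have been conducted within 90 days prior to enrollment".
- Section 4.1.6 requires white cells, hemoglobin, lymphocytes and platelets to meet thresholds within 90 days of enrollment.

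On prior treatment, Section 4.1.2 states: "Patients must be at least 28 days post cytotoxic chemotherapy, radiotherapy". Section 4.1.3 sets the same 28 days for systemic steroids. No section says that the qualifying CBC must come after such treatment ended.

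The narrative sections read differently. Section 3 says: "Clinical and autoimmune labs will be drawn prior to each vaccine", and it lists blood counts among the toxicity labs. Section 2.2 says that "all patients on study will be evaluated for acute autoimmune toxicity prior to each vaccination"; the list of tests that follows begins with a CBC with differential and gives marrow dysfunction as one of its purposes.

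**The concern.** Sections 2.2 and 3 describe a CBC and clinical labs before every vaccination. The schedule and visit text let the first one be skipped, and the condition for skipping is one that the eligibility criteria already impose. In practice the CBC at vaccine 1 is optional for nearly everyone.

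A single old CBC can then serve for eligibility, for the baseline visit and as the last count before a first-in-human vaccine. If the patient had recent chemotherapy or radiotherapy, that count may belong to a different marrow state. The error can go either way. A count from before treatment can make a treatment-related fall look vaccine-related. A count depressed by treatment can hide a fall after vaccination.

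Three uses in the plan lean on that reference count:

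- attribution of a low count to the vaccine, where a possible relation is enough under Section 8.5.1;
- follow-up of grade 3 or 4 toxicity until the patient is back at baseline (Sections 8.3 and 11.1.5);
- the Section 3 review of the first three patients in each arm before their second vaccine, on which enrollment of the rest of the arm depends.

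**Working it through.** The plan gives no figure of its own here. The check is interval arithmetic on its stated windows, plus one assumption.

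**Inputs**

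- Oldest qualifying CBC: 90 days before enrollment (4.1.6, 7.1 footnotes 1 and 5, 7.2).
- Minimum washout from chemotherapy or radiotherapy: 28 days before enrollment (4.1.2).
- Vaccine 1 to vaccine 2: 28 to 35 days (7.1 footnote 10).
- Labs for vaccine 2: up to 2 days before the visit (7.4.1), so the next scheduled CBC falls 26 to 35 days after vaccine 1 (28 − 2 = 26).
- Days from enrollment to vaccine 1, called g: not stated. I assume 0 to 21, borrowing the baseline-visit window in 7.2. Each further day of g would add one day to the figures below.

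**Step 1. Can the CBC date from treatment?** For a patient enrolled at the minimum washout, days −90 to −28 are open: 90 − 28 = 62 days, or 62/90 = 69% of the allowed window. A count from during treatment needs only that treatment was running on that day. A count from before treatment requires the whole course to fit inside those 62 days.

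**Step 2. How old is the count, and how far from the next one?** Worst-case age at vaccine 1 = 90 + g. Worst-case gap to the next CBC = 90 + g + (26 to 35).

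| g (assumed) | Age at vaccine 1 | Gap to next CBC |
|---|---|---|
| 0 | 90 days | 116 to 125 days |
| 7 | 97 days | 123 to 132 days |
| 14 | 104 days | 130 to 139 days |
| 21 | 111 days | 137 to 146 days |

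**Step 3. Comparison.** If the CBC is taken at the baseline visit, 0 to 21 days before vaccine 1, the gap is 0 + 26 = 26 to 21 + 35 = 56 days. If it is taken at vaccine 1 or up to 2 days before, the gap is 26 to 35 + 2 = 37 days, and the count falls at least 28 − 2 = 26 days after the last chemotherapy or radiotherapy.

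**Step 4. How far is the vaccine 2 count from treatment?** At least 28 + 0 + 28 − 2 = 54 days.

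**Step 5. Which count events reach the stopping rules?** The Section 8.5.1 table has seven entries, four of them blood counts. It is a list of exceptions: grade 3 lymphocyte or white cell decreases are allowed for 2 weeks, and platelet or hemoglobin decreases for 1 week. Within those durations they do not count toward the grade 3 benchmark, the patient-level rule or the three-participant rule. What remains is grade 4, where one attributable event ends accrual, and grade 3 that outlasts its allowance.

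**The case against.** The strongest reply is that the operative sections agree with each other. Sections 4.1.6, 7.1, 7.2 and 7.3 all use 90 days, and Section 7.3.1 keeps the metabolic panel, serologies, TSH and GAD65 at vaccine 1, so dropping only a recent CBC looks deliberate. Sections 2.2 and 3 are background and summary and give no windows. That explains the mismatch but does not remove it: Section 2.2 names the CBC among the tests before each vaccination, and no reason is given for treating it differently from the chemistry.

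Several stronger readings are tempting, and the documents do not support them.

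- A reader might infer that there is no valid baseline. Every eligible patient has a pre-vaccine CBC that met the 4.1.6 thresholds.
- A reader might infer that a low count at vaccine 2 cannot be told apart from the effect of earlier treatment. That count comes at least 54 days after treatment, history and concomitant medications are recorded, attribution is a five-level judgement, and further CBCs follow at vaccine 3 and at 1 and 6 months. Attribution is weakened, not ruled out.
- A reader might see that one patient is 10 percentage points in an arm of 10 and infer that three misattributed counts would end the study. The table exempts short-lived grade 3 count decreases, so three such events do not by themselves trigger the rule.
- A reader might infer that a new CBC would also repair eligibility. The 90-day eligibility window comes from 4.1.6 and would be unchanged.

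It also stands that CTCAE grades the count itself, that Section 13.4 plans no laboratory change-from-baseline analysis, and that the intervals above are worst cases. The documents do not say how many patients enroll soon after treatment, and sites may draw a CBC anyway.

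**Conclusion.** The point holds as a small but real defect. Current text conflicts on whether a CBC precedes the first vaccination, and the waiver lets the only pre-vaccine count come from during or before chemotherapy or radiotherapy. At worst that count is 90 to 111 days old at vaccine 1 and 116 to 146 days before the next scheduled one. A CBC at the baseline visit would bring the gap down to 26 to 56 days.

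These figures assume 0 to 21 days from enrollment to vaccine 1 and a CBC at the far edge of its window. The 62-day overlap applies in full only to a patient enrolled at the 28-day minimum and shrinks as time since treatment grows.

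The consequence is a possibly stale reference for attribution, for follow-up to baseline and for the three-patient review. Any effect on stopping is confined to grade 4 events and to grade 3 events that outlast the Section 8.5.1 allowances. How often this would arise cannot be worked out from the documents.

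**What to change.** Reconcile footnote 5 of Section 7.1 and Section 7.3.1.b with Sections 2.2 and 3 by removing the waiver. Take a CBC with differential and platelets from the blood already drawn at vaccine 1, or within 2 days as Section 7.3.1.c allows for the metabolic panel, and state that this is the pre-vaccine reference count for attribution and for return to baseline. The reference would then be at most 2 days old at vaccine 1, and the gap to the next CBC would be 26 to 37 days.

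The cost is two small text edits and one additional tube per patient. No visit or venipuncture is added, since the metabolic panel, the serologies and about 200 mL of research blood are already collected at that visit.
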